10.2 Adverse Events

As described in Section 3.2, four types of measures will be utilized to characterize participant safety and tolerability measures. First, as a part of the inter-operative and peri-operative data collection forms, information will be collected on surgical complications that characterize the risk and tolerability of the procedure itself. Second, participants will be asked about specific targeted complications on both the post-operative visit and a standard study evaluation collected at 6-month intervals (with those complications automatically populating the AE form. Third, participants will be asked through a response to open-ended questions to report any post-surgery adverse events to the study coordinator or physician at the 6-week visit and at the subsequent follow-up visits at 6-month intervals. If a serious adverse event, particularly a hospitalization, occurs, the participants will be asked to report that immediately to the study coordinator or physician. All adverse events are captured by the study coordinator on the adverse event logs. Finally, specific pain information is being collected as a part of all follow-up visits to characterize differences in post-operative pain beyond 6 weeks.

The group of measures collected inter-operatively and peri-operatively includes those in the table below. These measures include continuous measures as well binary and ordinal measures. For the

continuous measures, summaries will be presented by treatment arm that include mean levels and standard deviations and linear models with treatment as the primary predictor, controlling for site will be used to test for differences by treatment arm. For the binary and ordinal measures, summaries will included counts and percentages associated with each level of the binary or ordinal measure and Cochran-Mantel-Haenszel statistics and associated p-value with analyses stratified by site will be used to characterize differences in the treatment arms.

The AEs collected through the standard AE form will be summarized using standard contingency tables by treatment arm. These summaries will be provided by individual treatment-emergent AEs, AEs by body system, and AEs by subject. In addition to these general descriptions, specific comparison of risk and differences across the treatment arms will be evaluated for the outcomes listed in the table below.

Summary of Safety V	ariables				
Inter-operative and peri-operative measures					
Variable	Туре	Definition			
Operative time	Continuous	Obtained directly from peri-operative form			
Blood loss	Continuous	Obtained directly from peri-operative form			
Blood transfusion	Binary	Obtained directly from peri-operative form			
Complications	Ordinal	All complications will be collected and scored on a five- point ordinal scale using the Dindo classification scheme (Dindo, 2004). Each participant will then be classified according to the most severe complication			
Routinely Collected	Adverse Events				
Mesh-related Complications	Ordinal	Mesh related complications: mesh exposure in the vagina or mesh erosion into another organ; note that level of complication will be characterized into based on the following response classification schema: (a) None or non-surgical medical intervention only; (b) Minor or intra-office surgical intervention; (c) Outpatient surgery; (d) Inpatient surgery			
Pelvic infection	Binary	Any incident of pelvic infection will be captured as a Ye response (AE or SAE) to Question 13 in the complication section of the Hospitalization form or Question 14 of the follow-up evaluation form. It will also be captured base on open-ended AE responses with comments indicative pelvic infection.			
Perioperative infection	Binary	A perioperative infection will be captured as a Yes response (AE or SAE) to one or more of Questions 13, 14, 22, 23, 24, or 25 of the Hospitalization form or Questions 15, 16, 17, 18, 19, or 10 of the Post-operative visit form.			

UTI	Binary	A UTI will be captured as a Yes response (AE or SAE) to Question 23 of the Hospitalization form, Question 18 of the Post-operative visit form, or Question 20 or the 6- to 60- Month Study follow-up form or by an event classified as a Urinary Tract Infection based on Preferred terms in the AE form.		
Vaginal infections	Binary	A Vaginal Infection will be captured as a Yes response (AE or SAE) to Question 22 of the Hospitalization form, Question 17 of the Post-operative visit form, or Question 19 or the 6- to 60- Month Study follow-up form or by an event classified as a vaginal infection based on either the preferred term or comments for an event on the AE form.		
Vaginal shortening	Binary	Vaginal shortening will be determined by an event classified as a vaginal shortening based on either the preferred term or comments for an event on the AE form.		
De novo vaginal bleeding	Binary	Based on masked data review this event was modified from De novo vaginal bleeding to any incident of vaginal bleeding because of the small number of events. It will be captured as a Yes response (AE or SAE) to Question 17 on the 6- to 60- Month Study follow-up form or by an event classified as a vaginal bleeding based on either the preferred term or comments for an event on the AE form.		
Atypical vaginal discharge	Binary	Atypical vaginal discharge will be captured as a Yes response (AE or SAE) to Question 16 on the 6- to 60- Month Study follow-up form or by an event classified as atypical vaginal discharge based on either the preferred term or comments for an event on the AE form.		
Fistula formation	Binary	Fistula formation will be captured as a Yes response (AE or SAE) to Question 16 of the Hospitalization form, Question 8 of the Post-operative visit form, or Question 7 or the 6- to 60- Month Study follow-up form or by an event classified as a fistula based on either the preferred term or comments for an event on the AE form		
Neuromuscular problems	Binary	A neuromuscular problem will be captured as a Yes response (AE or SAE) to Question 12 of the Hospitalization form, Question 14 of the Post-operative visit form, or Question 13 or the 6- to 60- Month Study follow-up form or by an event classified as a neuromuscular disorder based on either the preferred term or comments for an event on the AE form		
Need for subsequent procedures	Binary	Need for subsequent procedures will be classified as Yes if the responses on Section E of the Post-operative visit form or Section D of the 6-to-60 Month Evaluation form indicated that the participant had a procedure performed in		

		the office in response to a complication from the surgery or the participant had a reoperation operating room for complication related to surgery, recurrent POP, SUI, or any gynecologic, vaginal, pelvic, or reproductive organ condition.
Uterine or cervical pathology	Binary	Classified as Yes based on masked review of AE preferred terms.
Vaginal scaring	Binary	Vaginal scarring will be determined by an event classified as a vaginal scarring based on either the preferred term or comments for an event on the AE form.
Dyspareunia	Binary	Defined via two different mechanisms: (a) as an event of dyspareunia as listed on AE form or the 6-month complication evaluation form; or (b) assessed via reporting on the PISQ-IR instrument. Note that because on masked review women moved in and out of the dyspareunia category after surgery, the decision was made to evaluate all incidents of dyspareunia irrespective of de novo status.

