The concept of creating a mesh suspension bridge to support the cervix and vaginal apex to bilateral sacrospinous ligaments was initially developed by Petros³¹ with the infracoccygeal sacropexy; however, the trocar delivery system and multifilament mesh resulted in unacceptably high complication rates and is no longer on the market. The concept of this procedure evolved from a trocar placed device to a trocarless placement, with the most recent product developed by Boston Scientific (Uphold® and Uphold® LITE). This procedure is performed through an anterior approach using a synthetic monofilament mesh bridge which attaches the cervix to this mesh and then bilaterally to the sacrospinous ligament (see Appendix A, Figure 1). It is essentially a mesh hysteropexy technique, although the FDA predicate approval process did not allow it to be promoted and marketed as such. The most recent FDA approval was September 14, 2011 for the Uphold® LITE Vaginal Support System indicated “for tissue reinforcement and stabilization of fascial structures of the pelvic floor for vaginal wall prolapse, where surgical treatment is intended, either as mechanical support or bridging material for the fascial defect.” The Uphold® LITE mesh has the same overall dimensions as the previous Uphold® mesh, but has a 75% increase in pore size, 38% reduction in weight, a 32% reduction in surface area ratio and is blue for enhanced visibility. As most literature would suggest that lighter, larger pore size mesh is preferable and may have less stress shielding (Moalli, AUGS, 2011), these changes are all considered positive, and for SUPeR we anticipate using the Uphold® LITE product. This Uphold® procedure results in a uterus in a more midline position with bilateral mesh sacral ligaments and theoretically is less likely to have suture pullout, asymmetry or extreme posterior deviation of the uterus. These mesh strap hysteropexy techniques allow the potential for decreased operative time and morbidity associated with hysterectomy. Theoretically, mesh exposure rates may be lower with these mesh strap hysteropexy techniques because of the smaller amount of mesh material used compared to other commonly performed anterior and posterior mesh kit procedures, the mesh straps are directed away from the vagina so that the mesh can be placed distant from incision lines.

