1. Hydrodissection of the vaginal walls will be performed with at least 30 cc of 0.25% bupivacaine with epinephrine or dilute Pitressin (20 Units/50-100 cc).
2. An approximate 4 cm transverse vaginal incision is made in the anterior vagina wall between the bladder neck and the cervix but at least 3 cm from the cervix so that the suture line will not overlap with the mesh.
3. Blunt or sharp dissection to approach the sacrospinous ligament extraperitoneally.
4. After confirmation of the location of the ischial spine, the tapered lead and mesh assembly will be delivered into the SSL 1-2 fingerbreadths medial to the ischial spine.
5. The most cephalic edge of the mesh will be attached to the cervix with sutures.

6. Mesh modifications (e.g. cutting) are strongly discouraged; any exceptions will be documented on operative case report forms.
7. Tensioning to re-suspend the apex without tense mesh arms.
8. Vaginal closure with 2-0 polyglactin.
9. Placement of a vaginal pack and Foley catheter removed on POD1.

For all procedures:

1. The study surgeon is responsible for meeting the experience requirements, is the surgeon of record, and will be present and scrubbed in for key portions of the procedure. Residents or fellows may participate in procedures as is standard for each Clinical Site.
2. Cystoscopy with intravenous indigo carmine dye (or an appropriate substitute) performed at the end of the procedure after all vault suspension sutures are tied or after the Uphold® straps are adjusted and is required as a standard part of the surgical procedure.
3. Prophylaxis against deep vein thrombosis is required for all participants. The method may be chosen by each surgeon.
4. Preoperative intravenous antibiotic prophylaxis is required as part of the surgical procedure. The details (choice of antibiotic, dose, etc.) will be determined by each surgeon.
5. All concomitant native tissue procedures must be declared and recorded prior to randomization. The surgeon has the discretion to alter from this preoperative plan as necessary to achieve the desired anatomic result. Any such alterations must be recorded.

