6. Anterior and posterior colporrhaphies will be performed at the discretion of the operating surgeon such that points Aa, Ba, Ap and Bp are less than or equal to -1 cm at the end of the procedure (i.e., anterior and posterior vaginal points located at least 1 cm above the hymen) at the end of the procedure. Colporrhaphies, when performed, will be performed with 2-0 or 0 delayed absorbable sutures. A non-straining POPQ examination will be performed and recorded at the end of the operative procedure and prior to cessation of anesthesia.

Surgery for Stress Urinary Incontinence

Stress continence outcomes are not a primary outcome in this study, and it is recognized that there is evidence to support universal or selective use of midurethral slings in the setting of vaginal operations for prolapse. Therefore, concomitant full length transobturator or retropublic midurethral slings will be allowed per the discretion of the surgeon. The placement of a midurethral sling should not have an effect on the primary outcome because tension-free

Confidential Please Do Not Copy

vaginal tape has been shown to not provide additional distal anterior vaginal wall support for patients undergoing total mesh colpopexy or laparoscopic colpopexy.^{44,45}

J.3 Masking of Randomized Intervention

Although the primary outcome does not depend on masked patients and blinded evaluators, several important patient-reported secondary aims are subject to patient reporting bias if the participant is aware of her group assignment. For example, in this current era of television advertisements recruiting patients for class action law suits against mesh manufacturers, many urinary, bowel, and sexual complaints are being attributed to transvaginal mesh and it is quite possible that if the participant knows that she has mesh she might be more likely to over-report these conditions. There are also significant internet testimonials that hysterectomy worsens sexual function and a patient's knowledge of having or not having a uterus could bias her reports on sexual function. For all these reasons, the ideal study design encourages masking and blinding to treatment assignment. There is precedent for achievable patient and evaluator blinding in RCT's of supracervical and total hysterectomies⁴⁶ and in this study, where the uterus is inactive, we think those successful blinding examples are relevant to this study design.

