7.2 Adjustments for Covariates

Indicator variables for the study stratification of site will be included as covariates in most efficacy analyses performed for this study (details in section 9). Additionally, demographic and baseline characteristics for subjects and clinicians will be compared between study arms using analysis of covariance techniques for continuous measures, Mantel-Haenszel mean score test using standardized midrank scores for ordinal measures, and Cochran Mantel-Haenszel chi-square tests for general association for categorical measures. If sample sizes allow, these analyses will control for the study stratification factors. If these analyses suggest that substantial differences exist among arms, the use as covariates of these parameters on which the arms differ will be explored in secondary exploratory analyses of the efficacy data.

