7.7 Multiple Comparisons and Multiplicity

There is only one formal hypothesis test for this study. As such, a statistical test will be conducted at a 5% type I error rate (two-sided) for the primary efficacy measure, and no adjustments for multiplicity other than control for the single interim analysis will be made. All analyses of secondary outcomes are exploratory in nature; therefore, p-values and confidence intervals are provided for descriptive purposes only. All p-values provided for any baseline and demographic characteristics and safety parameters will be for descriptive purposes only. As such, unless otherwise specified, p-values presented will be on a per analysis basis, with no further control for multiple tests.

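### Operative time and blood loss are compared with arm and site only; adding the repairs declared before randomization would be a nearly free gain in precision

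*SAP*

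**What the plan says.** **The model.** For the continuous intraoperative and perioperative measures, SAP 10.2 states that "linear models with treatment as the primary predictor, controlling for site will be used to test for differences by treatment arm". The table of safety variables in that section lists two such measures, operative time and blood loss, each "Obtained directly from peri-operative form". Site is the only stratification factor (Protocol H; SAP 4.3).

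**The declared plan.** Protocol J.2, under the rules for all procedures (item 5), says "All concomitant native tissue procedures must be declared and recorded prior to randomization". The next sentence adds: "The surgeon has the discretion to alter from this preoperative plan as necessary to achieve the desired anatomic result". Such changes must be recorded. Randomization takes place in the operating room immediately before surgery (Protocol H). Slings are handled in a separate paragraph of J.2: "midurethral slings will be allowed per the discretion of the surgeon".

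**Other covariate rules.** SAP 7.2 says of baseline characteristics that differ between the arms: "the use as covariates of these parameters on which the arms differ will be explored in secondary exploratory analyses of the efficacy data". The additional confounder models in SAP 9.4.3 apply to the functional efficacy outcomes. Neither rule covers operative time or blood loss.

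**Status of the outcomes.** Protocol B.1 says that mesh strap hysteropexy techniques "allow the potential for decreased operative time and morbidity associated with hysterectomy". Protocol M.2 puts both measures under Secondary Aim 2, to be reported in the primary outcome manuscript. SAP 7.7 states: "All p-values provided for any baseline and demographic characteristics and safety parameters will be for descriptive purposes only".

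**The concern.** Either arm may include anterior repair, posterior repair or perineorrhaphy, done in the same operation as the apical procedure. Extra surgical steps are likely to lengthen the operation and may plausibly add to blood loss, so women who differ in planned repairs probably differ in both outcomes whichever arm they are in. Randomization is stratified by site only, so planned repairs are balanced between the arms only by chance.

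The declared plan is fixed before allocation, which makes it a proper baseline covariate. Leaving it out keeps any variation it explains in the residual and widens the interval around the arm difference, for two outcomes on which the protocol suggests hysteropexy may have an advantage.

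There is also a case for settling the choice in the SAP. Both the declared plan and the changes to it are recorded. Without a rule, a later request to adjust for concomitant surgery could be met with the procedures performed. An unmasked surgeon can alter those after learning the arm, so they are not a baseline variable.

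**Working it through.** The plan gives no SD, expected difference, power or explained variance for operative time or blood loss, so there is no figure of its own to reproduce. The check below is in SD units.

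**Inputs**
- n = 88 and 87, total 175: the SAP perioperative table shell.
- 8 sites: SAP 7.4.
- R², the share of within-arm, within-site variance explained by the declared repairs: **assumed**, shown as a range.
- Two-sided 0.05 and 80% power: conventional, used only as a yardstick.

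**Arm and site only (R² = 0)**
- SE = √(1/88 + 1/87) = 0.151 SD.
- 95% CI half-width = 1.960 × 0.151 = 0.296 SD.
- Detectable difference = (1.960 + 0.842) × 0.151 = 0.424 SD.

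**Adding the declared repairs.** The SE is multiplied by √(1 − R²), and the equivalent sample size is 175/(1 − R²).

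| Assumed R² | SE multiplier | CI half-width (SD) | Detectable difference (SD) | Equivalent N |
|---|---|---|---|---|
| 0 | 1.000 | 0.296 | 0.424 | 175 |
| 0.02 | 0.990 | 0.293 | 0.419 | 179 |
| 0.05 | 0.975 | 0.289 | 0.413 | 184 |
| 0.10 | 0.949 | 0.281 | 0.402 | 194 |
| 0.20 | 0.894 | 0.265 | 0.379 | 219 |
| 0.30 | 0.837 | 0.248 | 0.354 | 250 |

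**Cost of three extra terms.** Residual degrees of freedom fall from 175 − 2 − 7 = 166 to 163, which inflates the SE by √(166/163) = 1.009, or about 0.9%. Break-even is where (1 − R²) × 166/163 = 1, so R² = 3/166 = 0.018. After this cost the SE multipliers for R² = 0.05, 0.10, 0.20 and 0.30 are 0.984, 0.957, 0.903 and 0.844.

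**What this means for power.** At a true difference of 0.424 SD, power rises from 0.80 to between 0.82 (R² = 0.05) and 0.92 (R² = 0.30). At a true difference of 1 SD it is about 1.00 with or without adjustment.

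**The case against.** The strongest reply is that nothing in the planned analysis is wrong. The model includes the only stratification factor, the comparison is randomized, and the p-values are descriptive. No alpha, power target or stopping guidance depends on either outcome. All of this stands, and it limits how much is at stake.

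Chance imbalance in planned repairs is ordinary sampling error that the unadjusted interval already covers. If a repair were declared in half the women and added 25 minutes (both assumed), a one-SD imbalance would be √(0.25 × (1/88 + 1/87)) = 0.076, shifting the difference by 0.076 × 25 ≈ 1.9 minutes. That is small.

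Time and bleeding come from what is done, not from what was declared. The plan may be altered, and site terms may already absorb part of the variation in repair practice. Both push R² down, which is why the range has to include values with little or no gain. Blood loss has a weaker case than operative time.

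Two limits on the covariate also stand. The declaration rule covers native tissue procedures and does not name slings, so any effect of slings stays in the residual. The safety population is grouped by treatment received (SAP 5), so plan and analysed group are strictly independent only if there are no crossovers.

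None of this shows harm from adjusting. At worst the SE rises by about 0.9%.

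**Conclusion.** The point holds as an improvement in precision at almost no cost; it does not correct an invalid analysis. For an assumed R² of 5–30%, the interval narrows by about 2.5–16% before the small degrees-of-freedom cost. At about 2% or less there is no gain. The size rests wholly on R², about which the documents say nothing.

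A reader might infer two stronger things. One is that the repairs are the main determinants of operative time and blood loss, so that a material loss of precision is certain. Neither document says this or gives data from which it could be judged; a contribution is likely for operative time and plausible for blood loss, and no more can be claimed. The other is that leaving the repairs out biases the arm comparison. It does not: the plan is declared before allocation, so the omission only widens a descriptive interval. The crossover caveat belongs to grouping by treatment received and applies with or without the covariate.

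**What to change.** In SAP 10.2, specify that operative time and blood loss are analysed with linear models containing treatment, site, and three indicators (anterior repair, posterior repair, perineorrhaphy) taken from the declaration made before randomization. State that procedures actually performed are not used as covariates. Report the adjusted arm difference with its 95% CI; the perioperative table shell has only a p-value column for the comparison. Note alongside the result that slings fall outside the declaration rule and that the groups are by treatment received.

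If perioperative results by arm have already been seen, keep the arm-and-site model as planned and label the adjusted model a sensitivity analysis. This needs checking first: the footer in the SAP table shells is dated 15 December 2018, after the first-lock visit cut-off of 16 February 2018 in SAP 4.4.2. SAP 2 already allows added exploratory analyses without an update to the plan.

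The cost is a sentence or two of SAP text and three degrees of freedom. The declaration is already recorded, but the documents do not show how it is coded, so confirm that the three repairs can be separated in the database.

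### The perioperative infection definition in SAP 10.2 lists Post-operative visit form Question 10, which appears to be a misprint for Question 20 and needs checking against the form

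*SAP*

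**What the plan says.** The Summary of Safety Variables table in SAP 10.2 defines each routinely collected adverse event by case report form item numbers. Perioperative infection is a binary variable. It is a yes to "one or more of Questions 13, 14, 22, 23, 24, or 25 of the Hospitalization form", or to "Questions 15, 16, 17, 18, 19, or 10 of the Post-operative visit form".

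Other rows of the table show how items on the two forms correspond:

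- Vaginal infections: "Question 22 of the Hospitalization form, Question 17 of the Post-operative visit form".
- Urinary tract infection: "Question 23 of the Hospitalization form, Question 18 of the Post-operative visit form".
- Fistula formation: Hospitalization Question 16 and "Question 8 of the Post-operative visit form".
- Neuromuscular problems: Hospitalization Question 12 and Post-operative Question 14.
- Pelvic infection: "Question 13 in the complication section of the Hospitalization form or Question 14 of the follow-up evaluation form". No Post-operative item is given.

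The urinary tract infection, vaginal infection and fistula rows also accept events coded on the AE form, and the pelvic infection row accepts open-ended AE responses. The perioperative infection row has no such second route.

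**The concern.** The Post-operative list rises from 15 to 19 and then drops to 10. The number expected next is 20, and the two explicit infection pairs in the table point the same way.

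This row is the specification a programmer would follow. Perioperative infection is a named safety outcome in Protocol M.2 (Secondary Aim 2) and SAP 3.2, and SAP 10.2 plans a specific comparison of it between arms. SAP 2 adds that these analyses feed a report on mesh surgery required by the FDA. If 10 is wrong and is programmed as printed, one source item is read from the wrong field. That can produce errors in both directions: infections left out, and events that are not infections counted. Because the row has no AE-form route, nothing else in the definition would recover an omitted event.

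**Working it through.** No power, alpha or sample-size figure is involved. The check is on item numbers, all taken from the SAP 10.2 table.

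**Step 1. Pairs stated outright.** Difference = Post-operative number minus the number on the other form. I take the follow-up form named in the pelvic infection row to be the 6- to 60-month form named in the other rows.

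| Row | Hospitalization | Post-operative | Difference | Follow-up form | Post-operative minus follow-up |
|---|---|---|---|---|---|
| Fistula | 16 | 8 | 8 − 16 = −8 | 7 | +1 |
| Neuromuscular | 12 | 14 | 14 − 12 = +2 | 13 | +1 |
| Pelvic infection | 13 | not given | – | 14 | – |
| Vaginal infection | 22 | 17 | 17 − 22 = −5 | 19 | −2 |
| Urinary tract infection | 23 | 18 | 18 − 23 = −5 | 20 | −2 |

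The difference is not constant across the forms. It is stable only within local blocks.

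**Step 2. The perioperative infection row, paired in listed order.**

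| Hospitalization | Post-operative as printed | Difference | Basis for the pair |
|---|---|---|---|
| 13 | 15 | +2 | next after 12/14 (neuromuscular) |
| 14 | 16 | +2 | next in the same block |
| 22 | 17 | −5 | stated (vaginal infection) |
| 23 | 18 | −5 | stated (urinary tract infection) |
| 24 | 19 | −5 | next after 23/18 |
| 25 | 10 | −15 | matches no other pair |

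Five of the six items fit. The sixth does not. With 20 in its place the difference is 20 − 25 = −5, and the list becomes 15 to 20 without a gap.

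**Step 3. A cross-check from the follow-up form.** Fistula and neuromuscular problems each sit one number higher on the Post-operative form than on the follow-up form (8 against 7, 14 against 13). Pelvic infection is Question 14 on the follow-up form, so the same step puts it at Post-operative Question 15, where the listed infection run begins. Question 10 falls before that run, between fistula (8) and neuromuscular problems (14).

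**Step 4. Who could be misclassified.** Suppose Question 20 is the intended infection item, Question 10 is not one, and the row is programmed as printed. Any yes on another listed item already classifies a woman as infected. The error is then confined to two groups:

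- women positive at Question 20 and at none of the printed items, who are omitted;
- women positive at Question 10 and at no true infection item, who are counted wrongly.

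The documents give no responses by item, so neither group can be sized.

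**The case against.** The strongest case against is that the form is not reproduced, so neither Question 10 nor Question 20 can be read. The SAP gives no explicit partner for Hospitalization 24 or 25. The offset is not uniform (+2 for neuromuscular problems, −8 for fistula), so five is not a rule for the whole form. Position is weak evidence too: the Hospitalization infection items are themselves split, at 13 and 14 and then 22 to 25, with fistula at 16 in between. An infection item at Post-operative Question 10 therefore cannot be excluded. A single digit can also be altered when a PDF is converted to text, so the SAP page itself should be looked at.

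All of this stands as a limit on certainty. It rules out three stronger readings that a reader might take from the sequence: that the SAP itself maps the item to Question 20, that Question 10 is shown not to be an infection item, and that infections will be lost. The first two are inferences. The third also depends on literal programming and on women with no other positive item. The limits do not remove the point, because the inference needs only the local block in which 22 and 23 pair with 17 and 18 and the listed 19 continues the run.

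It is also fair to say that the consequence is modest. SAP 10.2 has targeted complications from the post-operative visit populate the AE form automatically, so a Question 20 event could still appear in the general AE tables. Urinary tract and vaginal infections have their own rows. SAP 7.7 treats p-values for safety parameters as descriptive. None of this brings an omitted event back into the perioperative infection outcome.

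**Conclusion.** The point holds as a probable misprint in the working definition of a named safety outcome. Question 10 is out of sequence, has a difference of −15 seen in no other pair, and would fit if it read 20. The conclusion assumes that item order within the local infection block is the same on both forms. Any effect on results further requires that the program follows the printed number.

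The effect is limited to women whose classification rests on Question 10 or Question 20 alone. It cannot be expressed in events, and it touches no primary, efficacy or stopping analysis. The point is worth acting on because the definition feeds a comparison between arms and a regulatory safety report, has no fallback, and is quick to verify.

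**What to change.** Check the listed items against the Post-operative visit form. If confirmed, replace Question 10 in the perioperative infection row of SAP 10.2 with the correct infection item, probably Question 20. If Question 10 proves to be an infection item, say so in the row, and state which Post-operative item, if any, corresponds to Hospitalization Question 25. Then confirm that the analysis program reads that field, and rerun this one outcome if it was built on the printed number.

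The cost is one look at the form, a one-number correction and a check of one derived variable. No new data are needed.
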